6.3 Secondary Endpoints

- Change in CCS angina class
- Change in the score of all 5 domains of the Seattle Angina Questionnaire for assessing quality of life
- Change in the consumption and frequency of short acting nitrates (spray or sublingual tablets)
- Change in EBEST parameters at 4 months compared with baseline (total exercise duration, time to 1 mm ST segment depression, evidence of ischemia, peak exercise stage, peak exercise diastolic function and filling pressures as measured by echocardiographic E/e', and exercise-induced symptoms)

- Procedural-related Major Adverse Cardiac Events (MACE) defined as: death, myocardial infarction, perforation of the CS, CS total occlusion, or need for urgent dilatation of the Reducer within 4 months of follow-up

7- Study Population:

Patients with chronic refractory angina (CCS class II-IV), no obstructive CAD (<50% stenosis in epicardial vessels and/or iFR>0.89 or FFR>0.8 in vessels with 50 to 70% stenosis), and documented CMD (CFR≤2.5 and/or HMR≥2.5) & or coronary blood flow (CBF) response to acetylcholine ≤ 50%. on clinically indicated coronary angiography and invasive coronary reactivity testing which uses Adenosine, Acetylcholine & Nitroglycerin as standard clinical practice

7.1 Inclusion Criteria:

- Age ≥ 18
- Able to provide written informed consent and willing to participate in all required study follow-up assessments
- Symptomatic CAD with refractory angina defined as CCS class II to IV, despite optimal tolerated medical therapy for more than 3 months.
- Abnormal coronary microvascular function indices: CFR≤2.5 and/or HMR≥2.5 & or coronary blood flow (CBF) response to acetylcholine ≤ 50%.

7.2 Exclusion Criteria:

- Recent (within 3 months) acute coronary syndrome
- Recent (within 6 months) percutaneous coronary intervention revascularization by stent
- Patients with prior coronary artery bypass surgery

- Unstable angina (recent onset angina, crescendo angina, or rest angina with ECG changes) during the last 30 days
- Subjects in cardiogenic shock (systolic pressure < 80mm/Hg, on vasopressors or intraaortic counter pulsation) at the time of consenting. Subjects who recover from cardiogenic shock by the time of consenting are eligible.
- Obstructive CAD on coronary angiography (>70% stenosis or 50-70% stenosis with $iFR \leq 0.89$ or $FFR \leq 0.8$ in epicardial artery)
- Inability to perform invasive coronary flow evaluation and/or measure CFR and HMR in the LAD
- Severe valvular heart disease

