8.3 Subject Compliance Monitoring:

There will be no assessment of compliance as the device will be implanted in the cath lab, and there are no further drugs that need to be administered.

9- Coronary Reactivity Testing

A full clinically indicated coronary flow evaluation will be performed in the left anterior descending artery (LAD) as standard of care to determine study eligibility using an intracoronary combined Doppler-flow and pressure wire (ComboWire XT, Philips Volcano Corporation, Del Mar, California) that provides iFR/FFR, HMR and CFR measurements. In cases in which assessment cannot be performed in the LAD, coronary reactivity testing may be done in the left circumflex (LCx) artery. In brief, after engaging the coronary artery of interest with a guiding catheter, FFR or iFR will first be done in case of moderate (>50 to <70%) epicardial disease to document non-obstructive CAD (FFR>0.8 or iFR>0.89) as was previously described in section 2.4. In cases of mild (<40%) epicardial disease by angiography, FFR/iFR is not recommended but may be done at the discretion of the operator. After confirming non-obstructive epicardial CAD (no CAD, mild CAD<40% or negative FFR/iFR for moderate CAD >50 but <70%), the ComboWire XT will be inserted and parked in the mid LAD for measurement of CFR and HMR. Intracoronary bolus injections of incremental doses (36, 60 and 72 µg) of adenosine will be administered until maximal hyperemia is achieved or the largest dose was given ¹¹. CFR will be measured as the average hyperemic blood velocity post adenosine/average baseline velocity. Highest achieved CFR

will be used for analysis. A cine image of the LAD will be obtained after each adenosine administration. Coronary artery diameter will then be measured offline by an independent investigator in the segment 5 mm distal to the tip of the pressure-flow wire with a quantitative coronary angiography program (Medis Corp, Leiden, the Netherlands) as described previously^{46, 47} and coronary blood flow (CBF) will then be calculated from the Doppler-derived time velocity integral and vessel diameter, where $CBF = \pi \times (\text{coronary artery diameter}/2)^2 \times (\text{average peak hyperemic velocity}/2)$ ⁴⁸. HMR will then be calculated as distal coronary pressure divided by coronary blood flow at maximal hyperemia. For binary analysis, CMD will be defined as $CFR \leq 2.5$ and/or $HMR \geq 2.5$ ^{11, 12, 20, 21}.

10- Prior and Concomitant Therapy

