11.7 Post-Implant day 120 (± 14 days)

- Vital signs
- 12-lead ECG
- CCS angina class assessment
- SAQ assessment
- Adverse events
- Concomitant medications
- Limited physical exam
- Standard laboratory tests including hematology, blood chemistry, liver function tests, CRP and creatinine, urinalysis
- Evaluation of ischemia, exercise capacity, and left ventricular diastolic function and filling pressures at peak exercise on EBEST
- Coronary angiography and reactivity testing to measure CFR and HMR

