11.8 Schedule of Study Procedures and Assessments

Study Procedure/ Assessment	Screening	Enrolment/ Pre-Implant	Implant Day	Post-Implant			
Days	-30	-5 to -1	0	30	60	90	120

Windows				± 4	±7	±7	±14
Eligibility criteria	X						
Informed consent	X						
Medical history	X						
Vital signs	X	X	X				X
12-lead ECG	X	X	X				X
Standard laboratory tests including hematology, blood chemistry, liver function tests, CRP and creatinine, urinalysis.		X*					X
EBEST		X					X
CS Reducer Implant			X				
CCS Angina Class		X		X	X	X	X
SAQ		X		X	X	X	X
Coronary angiography to measure CFR and HMR							X
Physical exam	X						
Limited physical exam			X				
Adverse events	X	X	X	X	X	X	X

Concomitant medications	X						
-------------------------	----------	----------	----------	----------	----------	----------	----------

- a. CS Reducer will be implanted in the coronary sinus through right (preferably, or left internal jugular venous access)
- b. The patient will receive a phone call from the study coordinator to collect information on adverse events, angina class, SAQ, and concomitant medications.
- c. Vital signs will be measured prior to implant and every 8 hours until discharge
 - * Standard pre-procedural laboratory tests including hematology and blood chemistry including creatinine. Liver function tests, CRP, and urinalysis only at Day 120.

12- Statistical Plan

The effect of the CS Reducer implantation on microvascular function will be evaluated by the change in measured CFR and HMR at 4 months follow-up compared to baseline pre-CS Reducer implantation. Statistical analysis of the absolute and percent change in CFR and HMR measurements at follow-up will be done. Analysis of the delta change in CFR and HMR will also be performed. Change in angina intensity and frequency, and quality of life, will be evaluated by analyzing the change in CCS angina class, SAQ score in all five domains, and antianginals need and frequency from baseline to follow-up. Change in functional capacity will be evaluated as the change in baseline to follow-up EBEST total exercise duration, peak exercise stage, exercise-induced symptoms, and ischemic ECG and echocardiographic findings. Change in diastolic function and filling pressures will be evaluated as baseline to follow-up change in resting and peak exercise echocardiographic E/e' ratio.

All-completed population: Only subjects who completed ALL study related procedures and follow-up will be included in analysis.

13- Safety and Adverse Events

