13.10 Recording of Adverse Events

At each contact with the subject, the study team must seek information on adverse events by specific questioning and, as appropriate, by examination. Information on all adverse events should be recorded immediately in the source document, and also in the appropriate adverse event section of the case report form (CRF) or in a separate adverse event worksheet. All clearly related signs, symptoms, and abnormal diagnostic, laboratory or procedure results should be recorded in the source document.

All adverse events occurring during the study period must be recorded. The clinical course of each event should be followed until resolution, stabilization, or until it has been ultimately determined that the study device or participation is not the probable cause. Serious adverse events that are still ongoing at the end of the study period must be followed up, to determine the final outcome. Any serious adverse event that occurs after the study period and is considered to be at least possibly related to the study treatment or study participation should be recorded and reported immediately.

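### CS total occlusion counts towards procedural MACE, but no post-implant assessment is specified to establish whether the coronary sinus is patent

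*Combined protocol and SAP*

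**What the plan says.** **The endpoint.** Section 6.3 lists among the components of procedural-related MACE "perforation of the CS, CS total occlusion, or need for urgent dilatation of the Reducer within 4 months of follow-up". The synopsis lists the same components. Neither place defines CS total occlusion or names a method of confirming it.

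**Assessments after implant.**
- Days 30, 60 and 90 (Sections 11.4 to 11.6) are telephone contacts. The footnote to the schedule in Section 11.8 reads "The patient will receive a phone call from the study coordinator to collect information on adverse events, angina class, SAQ, and concomitant medications".
- Day 120 (Section 11.7) has vital signs, ECG, a limited examination, laboratory tests, an exercise echocardiogram and a catheterization. The catheterization is listed as "Coronary angiography and reactivity testing to measure CFR and HMR", and its row in Section 11.8 as "Coronary angiography to measure CFR and HMR".
- Section 9 describes what that test involves: "the ComboWire XT will be inserted and parked in the mid LAD for measurement of CFR and HMR", with the circumflex artery as the fallback.
- The exercise echocardiogram is specified as "Evaluation of ischemia, exercise capacity, and left ventricular diastolic function and filling pressures at peak exercise on EBEST". Neither the CS nor the device is mentioned.
- For adverse events generally, Section 13.10 says "the study team must seek information on adverse events by specific questioning and, as appropriate, by examination".

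**Where the CS is imaged.** Sections 7.2 and 8 are the relevant places. Angiography of the CS is named in Section 7.2 as an exclusion check on anatomy and diameter before implant. Section 8.1 states that the lumen at the centre of the device stays open, but argues this from the design of the device. Section 8.2 refers to a confidential Instructions For Use document for the implant steps.

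**The concern.** Most of the other MACE components (death, myocardial infarction, perforation, urgent re-dilatation) would come to notice clinically. Total occlusion of the CS is the component that depends most on someone looking at the vessel, and the visit schedule never asks anyone to look. Following the schedule exactly, an occlusion without symptoms has no planned route into the data, so the component is biased towards zero.

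This matters because MACE is the trial's only composite safety endpoint. It supports aim 5.4 (safety and feasibility) and the statement in Section 4 that implantation is safe. Aim 5.5 says the results will inform the design of pivotal studies. A zero that means *not looked for* could be carried forward as *did not occur*. The protocol itself treats occlusion as possible, since Table 1 lists it as a potential complication of the device.

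**Working it through.** The documents state no expected MACE rate, occlusion rate, precision target or analysis method for MACE, so there is no planned figure to reproduce. The check is a comparison of the endpoint with each scheduled assessment, followed by an illustration of what incomplete detection does to a count.

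**Step 1. Does any listed assessment ascertain CS patency after implant?**

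| Contact | What is specified | CS patency named? |
|---|---|---|
| Day 30, 60, 90 | Phone call: angina class, SAQ, adverse events, medication | No |
| Day 120 exercise echocardiogram | Ischemia, exercise capacity, diastolic function, filling pressures | No |
| Day 120 catheterization | CFR and HMR, wire in the mid LAD or the circumflex | No |
| Adverse-event enquiry | Questioning, and examination as appropriate | No |

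Imaging on the implant day, if the Instructions For Use require it, would not settle the matter. Section 8.1 says the narrowing and gradient are established 4 to 6 weeks after implantation, and the endpoint runs to 4 months.

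**Step 2. Do the earlier data make the check unnecessary?** Table 1 reports occlusion in 0/52, 0/204 and 0/1840. It does not say whether the CS was imaged in those series, so the zeros neither show that occlusion is rare nor show that it is common.

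**Step 3. Illustration of the effect on the count.** Inputs: n = 30 (Section 6.1). Two quantities are assumed because the documents give neither: the true occlusion rate p, and the share s of occlusions that reach the record.

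P(at least one recorded) = 1 − (1 − p·s)^30

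Example with p = 0.05 and s = 0.25: 1 − (1 − 0.0125)^30 = 0.314.

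| Assumed true rate p | s = 1 | s = 0.5 | s = 0.25 | s = 0 |
|---|---|---|---|---|
| 1% | 26.0% | 14.0% | 7.2% | 0% |
| 3% | 59.9% | 36.5% | 20.2% | 0% |
| 5% | 78.5% | 53.2% | 31.4% | 0% |
| 10% | 95.8% | 78.5% | 53.2% | 0% |

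**Step 4. What a reported 0/30 would mean.** With every CS read, the one-sided 95% upper limit on the true rate is 1 − 0.05^(1/30) = 9.5%. If only a share s is detected, the limit on the true rate is 9.5%/s:
- s = 0.5: 0.0950/0.5 = 19.0%
- s = 0.25: 0.0950/0.25 = 38.0%
- s = 0: no limit can be given

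Without a patency reading s is unknown, so the reader cannot tell which of these applies.

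**The case against.** The best reply is that the endpoint is labelled procedural-related, that its other components are mostly clinical, and that occlusion can reasonably be read as clinically detected occlusion. Every subject who completes follow-up has coronary angiography at Day 120, and Section 13 makes the investigator responsible for detecting adverse events through that visit. An occlusion might be noticed on those films. The case report forms and the Instructions For Use are not among the documents and might contain a relevant item. The stopping rule in Section 13.14 rests on device-related serious adverse events with DSMB review, not on this component.

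Much of this stands. A reader might infer that occlusion could be found only if symptoms led to other imaging. The documents do not support that, because incidental detection at Day 120 is possible. Nor does any rule say that an unassessed subject counts as event-free. That is an inference from the absence of a stated method and of a *not assessed* category.

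What the reply does not supply is a specified ascertainment. Incidental detection depends on how long the operator films and on whether anyone is asked to read the CS. If clinically detected occlusion is what is meant, Section 6.3 does not say so.

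**Conclusion.** The point holds in this form: CS total occlusion is a MACE component without a definition or a specified post-implant assessment. An asymptomatic occlusion would probably be missed, and a reported zero could not be taken as verified patency. The gap covers all implanted subjects, up to 30. The bias is towards zero, but its amount cannot be computed from the documents; the percentages in the working rest wholly on assumed rates and detection shares.

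Two stronger readings are tempting and should not be drawn.
- **CFR and HMR become uninterpretable.** An occlusion could affect that patient's values, but the primary endpoint is change after implantation, and nothing in the documents suggests a frequency that would threaten it.
- **The two-sided 95% upper limit for 0/30, 1 − 0.025^(1/30) = 11.6%, measures the defect.** It does not. It reflects 30 subjects and would apply even if every CS were imaged.

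The consequence is confined to one component of a secondary safety endpoint. It is still worth correcting, because an angiogram is already planned for each subject.

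**What to change.** **Preferred.** In Sections 11.7 and 11.8, have one of the left coronary cine runs already planned for Day 120 continue into the venous phase. Record CS patency as *patent*, *occluded* or *not assessed/not readable*. In Section 6.3, define CS total occlusion by reference to that reading. In Section 12, report the component with the number of subjects assessed as denominator and show the number not assessed beside it.

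The cost is slightly more cine time and radiation in a procedure already being done, and one CRF field. No new procedure is added. The documents do not say how often a venous-phase run would give a readable CS, so the investigator should confirm this; the third category covers the failures.

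**If that is not adopted.** Restate the component in Section 6.3 and the synopsis as *clinically apparent CS occlusion*, and state in the report that patency was not assessed. This is a text change only.

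Recording the position of the Reducer is optional. Position is not a MACE component, and this endpoint does not need it.

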11.8 Schedule of Study Procedures and Assessments

Study Procedure/ Assessment	Screening	Enrolment/ Pre-Implant	Implant Day	Post-Implant			
Days	-30	-5 to -1	0	30	60	90	120

Windows				± 4	±7	±7	±14
Eligibility criteria	X						
Informed consent	X						
Medical history	X						
Vital signs	X	X	X				X
12-lead ECG	X	X	X				X
Standard laboratory tests including hematology, blood chemistry, liver function tests, CRP and creatinine, urinalysis.		X*					X
EBEST		X					X
CS Reducer Implant			X				
CCS Angina Class		X		X	X	X	X
SAQ		X		X	X	X	X
Coronary angiography to measure CFR and HMR							X
Physical exam	X						
Limited physical exam			X				
Adverse events	X	X	X	X	X	X	X

Concomitant medications	X						
-------------------------	----------	----------	----------	----------	----------	----------	----------

- a. CS Reducer will be implanted in the coronary sinus through right (preferably, or left internal jugular venous access)
- b. The patient will receive a phone call from the study coordinator to collect information on adverse events, angina class, SAQ, and concomitant medications.
- c. Vital signs will be measured prior to implant and every 8 hours until discharge
 - * Standard pre-procedural laboratory tests including hematology and blood chemistry including creatinine. Liver function tests, CRP, and urinalysis only at Day 120.

12- Statistical Plan

The effect of the CS Reducer implantation on microvascular function will be evaluated by the change in measured CFR and HMR at 4 months follow-up compared to baseline pre-CS Reducer implantation. Statistical analysis of the absolute and percent change in CFR and HMR measurements at follow-up will be done. Analysis of the delta change in CFR and HMR will also be performed. Change in angina intensity and frequency, and quality of life, will be evaluated by analyzing the change in CCS angina class, SAQ score in all five domains, and antianginals need and frequency from baseline to follow-up. Change in functional capacity will be evaluated as the change in baseline to follow-up EBEST total exercise duration, peak exercise stage, exercise-induced symptoms, and ischemic ECG and echocardiographic findings. Change in diastolic function and filling pressures will be evaluated as baseline to follow-up change in resting and peak exercise echocardiographic E/e' ratio.

All-completed population: Only subjects who completed ALL study related procedures and follow-up will be included in analysis.

13- Safety and Adverse Events

The investigator will be responsible for the detection and documentation of any adverse events or serious adverse events as defined by this protocol. During the study there will be several safety evaluations and the investigator and/or site staff will be responsible for

detecting, documenting and reporting both adverse events and serious adverse events as defined by this protocol. These will be reported from the signing of the informed consent through the 4-month visit. Serious adverse events will be reported from the signing of the informed consent through the 4 month visit as well. Investigators will report any procedure or hospitalization to the Sponsor-Investigator to ensure any event needing adjudication can be done so in a timely fashion.

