Approximately, 30 subjects with angina, no obstructive CAD, and CMD invasively diagnosed by abnormal coronary flow reserve (CFR) and/or hyperemic microvascular resistance (HMR) will be enrolled in this single arm study. The primary objective is to evaluate the effect of CS narrowing using the Neovasc Reducer™ System on CFR and HMR at 4 months post Reducer implantation. Additional data will be collected on the adverse events and procedural success of the Reducer implantation procedure; as well as 4-months post-implant symptomatic and quality of life improvement as measured by the Canadian Cardiovascular Society (CCS) angina class, Seattle Angina Questionnaire short acting nitrates consumption frequency, functional capacity, intracardiac filling pressures, and ischemia as measured by exercise bicycle echocardiogram stress testing.

We hope that this study, the first of its kind in the USA using the CS Reducer as potential therapy for angina with no obstructive CAD (ANOCA) will address the therapeutic potential of CS narrowing for the treatment of CMD, an important unmet clinical need, and generate preliminary data for larger randomized phase 2 and 3 trials.

Study protocol

1- Introduction

This document is a human research study protocol. This study will be carried out in accordance with the applicable United States government regulations and Mayo Clinic research policies and procedures.

2- Background

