- Patients with chronic refractory angina (CCS class II-IV), no obstructive CAD (<50% stenosis in epicardial vessels and/or iFR>0.89 or FFR>0.8 in vessels with 50 to 70% stenosis), and documented CMD (CFR≤2.5 and/or HMR≥2.5) & or coronary blood flow (CBF) response to acetylcholine ≤ 50%.on clinically indicated coronary angiography and invasive coronary reactivity testing which uses Adenosine, Acetylcholine & Nitroglycerin as standard clinical practice will be eligible for enrolment.
- A full clinically indicated coronary flow evaluation will be performed in the left anterior descending artery (LAD) as standard of care using an intracoronary combined Doppler-flow and pressure wire (ComboWire XT, Philips Volcano Corporation, Del Mar, California) that provides iFR/FFR, HMR and CFR measurements. This will determine patient eligibility. If patients are deemed eligible, and wish to participate, they will go through the informed consent process to enroll in the study after their procedure.
- Baseline clinical evaluations of eligible patients will include clinical characteristics, medication profiles including antianginals, evaluation of angina severity and frequency by CCS angina class and Seattle Angina Questionnaire (SAQ), in addition to ischemia, exercise capacity, and left ventricular diastolic function and filling pressures at peak exercise on an exercise bike echocardiographic stress test (EBEST)

using a supine bike protocol starting at 25 Watts and increasing by 25 Watts every 2 minutes.

- Eligible patients will undergo percutaneous implantation of The Neovasc Reducer™ System (Neovasc Inc., Richmond, B.C., Canada) for the treatment of CMD.
- Adverse events will be collected during the 4 months study period and monthly follow-up phone calls with study participants will be conducted at 1, 2, and 3 months post CS reducer implant
- Study participants will undergo full repeat invasive evaluation of coronary blood flow and microvascular resistance (CFR and HMR) as well as repeat clinical evaluation (including CCS class, SAQ, antianginal medication use, adverse events, and EBEST) at 4 months following Reducer implantation.

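### The qualifying CFR/HMR test is the only baseline in a single-arm trial, so the Section 12 change includes regression to the mean, and a mean percent change would add a separate bias

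*Combined protocol and SAP*

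**What the plan says.** Section 12 (Statistical Plan) states: "The effect of the CS Reducer implantation on microvascular function will be evaluated by the change in measured CFR and HMR". It adds "Statistical analysis of the absolute and percent change in CFR and HMR measurements at follow-up will be done" and then "Analysis of the delta change in CFR and HMR will also be performed". It names no test, no summary statistic and no scale that decides.

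Section 6.1 describes an open-label, single-arm design. Of the clinically indicated LAD test that yields CFR and HMR, it says: "This will determine patient eligibility". Patients who are eligible and willing come after that: "they will go through the informed consent process to enroll in the study after their procedure". Section 9 also says the test determines eligibility.

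The screening list (11.1), the pre-implant list (11.2) and the implant-day list (11.3) contain no CFR or HMR measurement. The schedule (11.8) marks it at Day 120 only.

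Entry routes are not described uniformly. Section 7.1 accepts abnormal CFR and/or HMR "or coronary blood flow (CBF) response to acetylcholine" at or below 50%. The Project Summary describes patients with "CMD invasively diagnosed by abnormal coronary flow reserve (CFR) and/or hyperemic microvascular resistance (HMR) will be enrolled in this single arm study". Section 9 likewise uses only those two indices: "For binary analysis, CMD will be defined as" CFR at or below 2.5 and/or HMR at or above 2.5.

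**The concern.** When patients are chosen because a noisy measurement crossed a threshold, a second measurement drifts back toward the population mean even if nothing has changed. Here the value that selected the patient is also the baseline, there is no second pre-implant value, and no control arm shows how large the drift is. Section 12 nevertheless reads the change as the effect of the device.

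The trial is presented as a study of potential efficacy that yields preliminary data, so a confirmatory claim is not at stake. What matters is what follows from it: Aim 5.5 says the trial will supply the information needed to design pivotal studies. A change inflated by selection could become the assumed effect there.

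A second, smaller problem is the percent scale. Measurement error in the denominator pushes the average of individual percent changes upward. Upward means benefit for CFR and harm for HMR, so the two primary measures would be biased in opposite clinical directions.

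**Working it through.** The plan has no figure to reproduce: the 30 patients come without alpha, power, effect size, SD or repeatability.

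**Step 1: which baseline.** Sections 6.1 and 9 place the CFR/HMR test before consent and make it decide eligibility. Sections 11.1 to 11.3 and 11.8 schedule no other before implant. Baseline can only be the qualifying value.

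**Step 2: direction, without assumed sizes.** With no device effect and two exchangeable measurements, the mean change over everyone tested is zero. The excluded patients all measured CFR above 2.5 and HMR below 2.5, so as a group their CFR tends to fall and their HMR to rise on repeat. The eligible patients, taken together, must balance this: CFR rises and HMR falls, which is toward apparent benefit. The shift reaches zero only when nobody is excluded on these criteria. Within the eligible group, acetylcholine-only entrants also measured normal on both indices, so they move the unfavourable way.

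**Step 3: assumed inputs.** None is in the documents: tested-population CFR mean 2.8, SD 0.7; HMR mean 2.1, SD 0.7; lognormal; correlation -0.4 between true log values; error correlation -0.4 or 0; ICC 0.5 to 0.85; acetylcholine positivity independent of CFR and HMR; zero device effect.

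On the log scale, variance = ln(1 + (SD/mean)²) and location = ln(mean) - variance/2.
- CFR: variance ln(1.0625) = 0.0606, SD 0.246, location 0.999.
- HMR: variance ln(1.1111) = 0.1054, SD 0.325, location 0.689.
- Threshold: ln(2.5) = 0.916. Then z = -0.337 for CFR (36.8% qualify) and 0.699 for HMR (24.2% qualify).

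**Step 4: shift on the qualifying index.** The expected log change has size (1 - ICC) × SD × φ(z)/P, where P is the qualifying fraction. SD × φ(z)/P is 0.252 for CFR and 0.419 for HMR.
- CFR in CFR qualifiers: exp(0.5 × 0.252) = 1.13 at ICC 0.5; exp(0.15 × 0.252) = 1.04 at ICC 0.85.
- HMR in HMR qualifiers: exp(-0.5 × 0.419) = 0.81; exp(-0.15 × 0.419) = 0.94.

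**Step 5: whole trial.** In this model up to 53% of tested patients meet neither the CFR nor the HMR criterion. If a fraction q is acetylcholine-positive, the acetylcholine-only share of entrants is 0.53q/(0.47 + 0.53q). For q = 0.3 this is 0.159/0.629 = 25%; for q = 0.5 it is 0.265/0.735 = 36%; for q = 1 it is 53%. Simulated trials of 30, with a one-sample t-test at two-sided 5% (nominal 2.5% in the favourable direction), gave:

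| Acetylcholine-only share | Absolute CFR change | Absolute HMR change | False improvement, CFR | False improvement, HMR |
|---|---|---|---|---|
| 0% (entry as in the Project Summary) | +0.05 to +0.24 | -0.04 to -0.21 | 14-57% | 7-31% |
| 25-36% | +0.02 to +0.12 | -0.01 to -0.11 | 4-17% | 4-12% |
| 47% (q = 0.8) | at most +0.03 | at most -0.02 | 3-4% | 3-4% |
| 53% (q = 1) | 0 | 0 | 2.5% | 2.5% |

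A second model used median CFR 2.7, median HMR 2.0, between-patient CV 25%, within-patient CV 10-25% and a weakly correlated acetylcholine response. With all eligible patients enrolled it gave CFR +0.03 to +0.14 and HMR -0.02 to -0.09. Acetylcholine-only entrants moved the other way (CFR -0.17, HMR +0.11 at CV 15%).

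**Step 6: percent scale, no selection at all.** The mean of follow-up/baseline, minus 1, is exp{(1 - ICC) × variance} - 1.
- CFR: exp(0.0091) - 1 = +0.9% at ICC 0.85; exp(0.0303) - 1 = +3.1% at ICC 0.5.
- HMR: exp(0.0158) - 1 = +1.6%; exp(0.0527) - 1 = +5.4%.
- False CFR improvement: about 4-7%.

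**The case against.** The strongest reply is that this is a small, openly preliminary study, that no repeatability is given, and that good reproducibility would make the shift minor. The first part limits the consequence but does not answer Aim 5.5 or the wording of Section 12. The second stands in part: the sizes are assumptions, and at ICC 0.85 with a substantial acetylcholine-only share the shift is small. The direction by route does not depend on those sizes.

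Three stronger readings are tempting, and the documents do not support them.
- A reader might infer that the net direction is simply unknown, or could equally run against the device. With natural enrolment it favours benefit or falls to zero. Reversal needs acetylcholine-only patients to be over-represented, which no section describes. Imposing a 65% share does reverse it (CFR -0.01 to -0.06), but under these inputs natural enrolment cannot exceed 53%. That ceiling is itself a product of the assumptions.
- A reader might infer that any percent summary is biased. The bias belongs to the arithmetic mean of individual percent changes. A percent change of group means does not carry it, nor does the median in an unselected pool. Section 12 does not say which is meant.
- A reader might infer that absolute and percent HMR results will contradict each other. Opposite signs occur in 13-34% of zero-effect trials, but these are means close to zero. In 20,000 simulated trials per scenario, none combined opposite signs with a significant test on either scale.

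The study flow chart is not reproduced in the available text. The written sections and the schedule contain no second baseline.

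**Conclusion.** The concern holds. The change from a qualifying value in an uncontrolled trial includes regression to the mean, and Section 12 presents it as the effect of implantation without qualification. The size runs from material, when entry is on CFR or HMR alone, to negligible, when about half of entrants qualify on acetylcholine alone. The documents leave that mix open because Section 7.1 differs from the Project Summary and Section 9, and those passages must be reconciled.

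The percent-scale bias is separate, smaller, and conditional on an arithmetic mean being used. It favours the device on CFR and works against it on HMR.

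This should be fixed, but it does not invalidate the trial. Confidence is medium: the structure is clear from the text, while every magnitude rests on assumed means, SDs, ICC and correlations.

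**What to change.** In Section 12:

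1. Replace percent change with log(follow-up/baseline), reported as a geometric mean ratio with 95% CI. Name it as the deciding scale for CFR and for HMR, with absolute (delta) change as supportive. This removes the percent-scale bias; it does not remove regression to the mean.
2. Report, descriptively, the number of patients and the change by qualifying criterion: CFR, HMR, both, acetylcholine only.
3. Replace the sentence that reads the change as the effect of implantation. State instead that the uncontrolled change from a qualifying value includes regression to the mean, is not by itself an estimate of device effect, and should not be carried unadjusted into pivotal-trial design.

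Reconcile the entry-route descriptions in Section 7.1, the Project Summary and Section 9.

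Optional: a sensitivity analysis that compares the 95% confidence limit nearer to no change with the shift expected for the actual entry mix, over declared ranges of ICC and error correlation. It depends on the site's existing test results being available for this use. Section 7.3 says 8-10 such tests are done a month, but not that the results are held in analysable form. It also needs an ICC floor that the sponsor must choose without data, so statisticians may reasonably differ on including it.

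Cost: analysis wording, a little more analysis work and a less favourable conclusion. No new patients or procedures are needed.
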